# 6. Benefits

a. Description of the probable benefits for the participant and for society.

No direct benefits for study subjects, but the results of this work may improve care of future bariatric patients.

# 7. Payment and Remuneration

a. Detail compensation for participants including possible total compensation, proposed bonus, and any proposed reductions or penalties for not completing the protocol.

There is no compensation to participate in this study. We are randomizing patients to standard of care dressing versus the Prevena Wound VAC dressing (which is being provided by the sponsor). There are no extra visits or extra time involved above and beyond the standard of care for the patient.

#### 8. Costs

a. Detail costs of study procedure(s) or drug(s) or substance(s) to participants and identify who will pay for them.

Costs of the Prevena Wound VAC and the microbiology swabs are being covered by the study. Participants (or insurance) are responsible for paying the cost of the routine standard of care and follow-up clinical examination visits that are included following bariatric surgery.

#### APPENDIX A (SF-36 Questionnaire)

Standard Form – 36 (SF-36)	
Patient Name:	Date:
Standard Form 36 Survey: The SF-36 Form is one of ma Outcomes Trust in Boston, MA. It is designed to approxim intervention.	
INSTRUCTIONS: This survey asks for views about track of how you feel and how well you are able to question marking the answer as indicated. If you are give the best answer you can.	

 
In general, would you say your health is: (Circle One)
 
	
 
Excellent
 
Very Good
 
Good
 
Fair
 
Poor
 

2. Compared to one year ago, how would you rate your health in general at this time? (Circle One)	
 
Much better now than one year ago
 
Somewhat better now than one year ago
 
About the same as one year ago
 
Somewhat worse than one year ago
 

 5. Much worse now than one year ago
 3. The following items are about activities you might do during a typical day. Does your health now limit you in these activities? If so, how much? (Circle the appropriate number for each question)

Activities	Yes, limited a lot	Yes, limited a little	No, not limited
a. Vigorous activities, such as running, lifting heavy Objects, or participation in strenuous sports	1	2	3
b. Moderate activities, such as moving a table, Vacuuming, bowling or golfing	1	2	3
c. Lifting or carrying groceries	1	2	3
d. Climbing several flights of stairs	1	2	3
e. Climbing one flight of stairs	1	2	3
f. Bending, kneeling, or stooping	1	2	3
g. Walking more than a mile	1	2	3
h. Walking several blocks	1	2	3
i. Walking one block	1	2	3
j. Bathing or dressing yourself	1	2	3

4. During the past 4 weeks, have you had any of the following problems with your work or other regular activities as a result of your physical health? (Circle the appropriate number for each question)				
a. Cut down on the amount of time you spent on work or other activities	Yes = 1	No = 2		
b. Accomplished less than you would like	Yes = 1	No = 2		
c. Were limited in the kind of work or other activities	Yes = 1	No = 2		

 
d. Had difficulty performing the work or other activities (For example – requiring an extra effort)
 
	Yes = 1	No = 2		

5. During the past four weeks, have you had any of the following problems with your work or other regular daily activities as result of any emotional problems (such as feeling depressed or anxious)? (Circle the appropriate number for each question)

a. Cut down on the amount of time you spent on work or other activities	Yes = 1	No = 2
b. Accomplished less than you would like	Yes = 1	No = 2
c. Didn't do work or other activities as carefully as usual	Yes = 1	No = 2

6. During the past 4 weeks, to what extent has your physical health or emotional problems interfered with your normal social activities with family, friends, neighbors or groups? (Circle one)	2 Slightly
---	------------

 
How much bodily pain have you had during the past 4 weeks? (Circle one)
 
	3. 4. 5.	None Very mild Mild Moderate Severe
	6.	Very severe

8. During the past 4 weeks, how much did pain interfere with your normal work (including both work outside the home and housework)? (Circle one)				2. S 3. M 4. Qu	ot at all lightly loderately lite a bit tremely	
9. These questions are about how you feel and how things have been with you during the past 4						the past 4
weeks. For each question, please give th	e one an	swer that	comes clo	sest to the	way you	have been
feeling. How much of the time during the	past 4 w	eeks: (Cir	cle one nu	umber on e	each line)	
	All of	Most of	A good	Some	A little	None of
	the	the	bit of the	of the	of the	the time
	time	time	time	time	time	
a. Did you feel full of pep?	1	2	3	4	5	6

b. Have you been a very nervous person?	1	2	3	4	5	6
c. Have you felt so down in the dumps that nothing could cheer you up?	1	2	3	4	5	6
d. Have you felt calm and peaceful?	1	2	3	4	5	6
e. Did you have a lot of energy?	1	2	3	4	5	6
f. Have you felt downhearted and blue?	1	2	3	4	5	6
g. Did you feel worn out?	1	2	3	4	5	6
h. Have you been a happy person?	1	2	3	4	5	6
i. Did you feel tired?	1	2	3	4	5	6

10. During the past 4 weeks, how much of the time has your physical health 1. All of the time or emotional problems interfered with your social activities (like visiting friends, relatives etc.)?(Circle one)

2. Most of the time

3. Some of the time

4. A little of the time

5. None of the time

	Definitely True	Mostly True	Don't Know	Mostly False	Definitely False
a. I seem to get sick easier than other people	1	2	3	4	5
b. I am as healthy as anybody I know	1	2	3	4	5
c. I expect my health to get worse	1	2	3	4	5
d. My health is excellent	1	2	3	4	5

#### APPENDIX B (Short-Term Prevena Recovery Form)

#### Short-Term Prevena Recovery Form

POD#1POD#2Condition at DischargeSeal intact Y/NDrainage Amount (in ml)Drainage type (Serosang, Sang, Serous, Purulent)Odor Y/NErythema Y/NEcchymosis Y/NEdema Y/NSeroma Y/NIncision intact Y/NPatient's tolerance to VAC1=excellent 2=good 3=fair 4=poorNPO Y/NVoiding Y/NLast name of person completing evaluation	Pt Initials	Bayview No	Date of o	operation	Width of foam used:
Drainage Amount (in ml)Image Amount (in ml)Drainage type (Serosang, Sang, Serous, Purulent)Image Amount (in ml)Odor Y/NImage Amount (in ml)Codor Y/NImage Amount (in ml)Erythema Y/NImage Amount (in ml)Edema Y/NImage Amount (in ml)Edema Y/NImage Amount (in ml)Edema Y/NImage Amount (in ml)Seroma Y/NImage Amount (in ml)Incision intact Y/NImage Amount (in ml)Patient's tolerance to VACImage Amount (in ml)Image Amount (in ml)		POD#1	POD#2		7
Drainage type (Serosang, Sang, Serous, Purulent)Image: Serous of the service of th	Seal intact Y/N				7
Serous, Purulent)       Odor Y/N         Odor Y/N       Erythema Y/N         Erythema Y/N       Edema Y/N         Edema Y/N       Seroma Y/N         Incision intact Y/N       Incision intact Y/N         Patient's tolerance to VAC       1         1=excellent       2=good         3=fair       4=poor         NPO Y/N       Voiding Y/N         Last name of person completing       Incision	Drainage Amount (in ml)				7
Erythema Y/N     Image: Constraint of the second seco		Sang,			-
Ecchymosis Y/N     Edema Y/N       Edema Y/N     Incision intact Y/N       Seroma Y/N     Incision intact Y/N       Patient's tolerance to VAC     Incision intact Y/N       1=excellent     Incision intact Y/N       2=good     Incision intact Y/N       3=fair     Incision intact Y/N       VPO Y/N     Incision intact Y/N       Voiding Y/N     Incision intact Y/N       Last name of person completing     Incision intact Y/N	Odor Y/N				7
Edema Y/N     Incision intact Y/N       Incision intact Y/N     Incision intact Y/N       Patient's tolerance to VAC     Incision intact Y/N       1=excellent     Incision intact Y/N       2=good     Incision intact Y/N       3=fair     Incision intact Y/N       Voiding Y/N     Incision intact Y/N       Last name of person completing     Incision intact Y/N	Erythema Y/N				7
Seroma Y/N Incision intact Y/N Patient's tolerance to VAC 1=excellent 2=good 3=fair 4=poor NPO Y/N Voiding Y/N Last name of person completing	Ecchymosis Y/N				7
Incision intact Y/N Patient's tolerance to VAC 1=excellent 2=good 3=fair 4=poor NPO Y/N VI Voiding Y/N IIIIIIIIIIIIIIIIIIIIIIIIIIIIIIIIIII	Edema Y/N				7
Patient's tolerance to VAC 1=excellent 2=good 3=fair 4=poor NPO Y/N Voiding Y/N Last name of person completing	Seroma Y/N				1
1=excellent       2=good       3=fair       4=poor       NPO Y/N       Voiding Y/N       Last name of person completing	Incision intact Y/N				1
Voiding Y/N Last name of person completing	1=excellent 2=good 3=fair 4=poor	c			_
Last name of person completing					_
	Last name of person com evaluation				_
Time to first ambulation following surgery (specify unit please): Comments					

#### Appendix C (Long-Term Prevena Recovery Form)

#### Long-Term Prevena Recovery Form

Pt Initials Bayview No	Date of operation
	POD#30
Incision Closed/Intact Y/N	
Incision Redness Y/N	
Skin Discoloration Around Incision Y/N	
Incision Foul Odor Y/N	
Incision Painful/ Swollen Y/N	
Incision Leaking Blood/Pus Y/N	
Fever/Chills Y/N	
Change in Bowel Habits Y/N	
If Yes Diarrhea/Constipation	
Patient's Overall Experience	
1=excellent	
2=good	
3=fair	
4=poor	

Date of Interview\_\_\_\_\_

Was the interview by: Phone\_\_\_\_\_ Personal Interview \_\_\_\_\_

Comments\_

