**Hypothesis 2A:** Obese patients who have the Prevena system applied to their incision will have a lower bacterial skin count upon removing Prevena on post-operative day #5-7 as compared to those who had a standard of care dressing placed.

**Specific Aim 3:** To determine whether obese patients who have incisional wound PrevenaTM applied during their surgical procedure have better quality of life assessment as compared to those obese patients who have a standard of care dressing.

**Hypothesis 3A:** Obese patients who have the Prevena system applied to their incision will experience less wound complications and improved quality of life scores using the SF-36 (appendix A).

**Specific Aim 4:** To determine whether obese patients who have an incisional wound PrevenaTM applied during their surgical procedure have decreased readmission rates compared to those obese patients who have a standard of care dressing.

**Hypothesis 4A:** Obese patients who have the Prevena system applied to their incision will experience a decreased readmission rate within 30 days of the operation.

**The primary outcome measure:** the incidence of postoperative surgical site infection (according to CDC/NHSN protocol) in open surgery.

**The secondary outcome measures:** other wound complications (such as dehiscence, seroma and hematoma), skin bacterial count after treatment, wound healing time, quality of life reporting and readmission rates between the two groups.

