# Follow Up

The patient will be advised to contact the hospital if any of the following signs develop at any time after the procedure (before and in between follow ups):

- a. Fever
- b. Warm, red, painful, swollen wound
- c. Blood or pus coming from the wound
- d. Foul odor coming from the wound

- 1) **POD #1-2:** The patient will receive a personal interview within 24-48 hours of the surgery while still hospitalized by an RN. A Short-Term Prevena Recovery Questionnaire (appendix B) will be completed during the interview regarding the patient's recovery. The most important questions will be tailored towards identifying any allergic reaction symptoms to the treatment option. Other questions include: tolerance, nutrition habits, voiding and bowel movements and any signs of wound infection.
- 2) **POD #5-7:** An examination by an independent nurse practitioner or physician assistant who is blinded to the treatment groups will be performed. Any surgical site infections or complications will be diagnosed using the Center for Disease Control and Prevention guidelines. If there are any complications (i.e. delayed healing, infection), the patient will be scheduled for weekly follow up with the NP, PA or MD until complete wound healing.
- 3) **POD #12 to 14:** Patients will return to clinic for staple or suture removal by the surgeon, the NP or PA. A secondary wound assessment will be performed as in step (2). In the same visit an SF-36 questionnaire (appendix A) will be completed by the patient to evaluate the therapy's impact on QOL.
- 4) POD # 30± 5 days: The patient will receive a phone call or personal interview (if still hospitalized) from one of our team members. A Long-Term Prevena Recovery Questionnaire (appendix C) will be completed during the calls regarding the patient's recovery. Questions about any possible wound complications include: incision check-up (changes in wound appearance and any of the signs mentioned above), development of any new symptom (fever, bowel habit changes, and nutrition habits).

Note: This time frame for follow up was chosen because:

- a. It will minimize data lost to follow up.
- b. It will maximize the opportunity for detection of infection, since the majority of SSIs are apparent by postoperative day 3-5.
- c. The standard of care at the Johns Hopkins surgical department includes a post-op check and visit 5 to 14 days following surgery.
- b. Study duration and number of study visits required of research participants.

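### Appendix C, the last scheduled SSI check, states no recall period, asks nothing about diagnosis or treatment since POD 12-14, and merges blood with pus, so settled late infections may be missed

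*Combined protocol and SAP*

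**What the plan says.** The primary outcome (section 2, Objectives) is "the incidence of postoperative surgical site infection (according to CDC/NHSN protocol) in open surgery". Hematoma is among the secondary wound complications.

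Under Study Procedures, Follow Up, wounds are examined at POD 5-7 and again at POD 12-14, when staples or sutures come out. Weekly visits follow only if a complication is found. The final contact is at POD 30 ± 5 days: "The patient will receive a phone call or personal interview (if still hospitalized) from one of our team members". On the instrument, the protocol says: "A Long-Term Prevena Recovery Questionnaire (appendix C) will be completed during the calls regarding the patient's recovery". It describes the wound questions as "incision check-up (changes in wound appearance and any of the signs mentioned above), development of any new symptom".

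Appendix C has one column, headed POD 30. Its yes/no rows cover incision closure, redness, discoloration, odor, pain or swelling, leakage, fever or chills, and bowel change. An overall rating and a Comments line complete it. The leakage row is "Incision Leaking Blood/Pus Y/N". The Follow Up list of signs that should prompt a patient to call has the same pairing: "Blood or pus coming from the wound". Appendix B, used at POD 1-2, instead records the type of drainage, with purulent as a category separate from sanguineous.

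**The concern.** Incidence is a count of events over an interval, so the instrument covering the last part of that interval has to ask about the interval. Appendix C does not say what period its rows cover. One caller may ask how the wound is today and another how it has been since the last visit. It has no row for the facts that would reveal an infection already dealt with: a diagnosis, an opening or drainage of the incision, or a course of antibiotics. A patient infected on POD 18, treated elsewhere and healed by the call could complete it without the event appearing.

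The leakage row has a separate weakness. Pus points towards the primary outcome, while blood may point towards hematoma, a secondary outcome. A Yes does not say which.

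At stake is complete and specific capture of the one outcome on which the trial is sized.

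**Working it through.** **1. What covers the late interval.** The last scheduled examination is at POD 12-14 and the final contact is at POD 25-35 (30 ± 5). The gap is between 25 − 14 = 11 and 35 − 12 = 23 days. For a patient without an earlier complication, the only scheduled SSI contact after that examination is the one at which Appendix C is completed.

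**2. What the form can record, set against what is needed.**
- *Recall period:* none stated on the form. The Follow Up text refers to changes and new symptoms but sets no starting date.
- *Onset date:* no row.
- *SSI diagnosis, wound opening or drainage, antibiotics:* no row.
- *Pus v blood:* one row in Appendix C; separate categories in Appendix B.
- *Route from a Yes to a CDC/NHSN SSI:* not stated anywhere.

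**3. The plan's sample size.** Inputs from Study Statistics, item c: 20% v 3%, alpha 0.05, 80% power, 54 per group. Sidedness is not stated; two-sided is assumed here. The pooled two-proportion formula without continuity correction gives 55 per group, in line with the stated 54. (One-sided with continuity correction gives 54.) Power at n = 54:

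power = Φ[(d − 1.96 × SE0) / SE1], where SE0 = √(2 p̄(1 − p̄)/n) and SE1 = √((p1(1 − p1) + p2(1 − p2))/n)

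- d = 0.20 − 0.03 = 0.17; p̄ = 0.115
- SE0 = √(2 × 0.115 × 0.885/54) = 0.0614
- SE1 = √((0.1600 + 0.0291)/54) = 0.0592
- (0.17 − 1.96 × 0.0614)/0.0592 = 0.839, so power = 79.9%

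**4. Illustration of lost events.** The documents give no share of SSIs that arise after POD 14 and settle before the call. Assume that 10-30% arise late and half of those have settled and go unrecorded, equally in both arms. Then 5-15% of events are lost.

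| Events lost | Control | Prevena | Difference | Power, 54 per arm |
|---|---|---|---|---|
| 0% | 20.0% | 3.00% | 17.00 points | 79.9% |
| 5% | 19.0% | 2.85% | 16.15 points | 77.5% |
| 15% | 17.0% | 2.55% | 14.45 points | 72.1% |

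In counts, the plan expects 54 × 0.20 + 54 × 0.03 = 10.8 + 1.62 = 12.42 events. A loss of 5-15% is 0.6 to 1.9 of them. Because the loss is assumed equal in the arms, the risk ratio stays at 0.15; what shrinks is the absolute difference and the power.

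**5. The blood/pus row.** No power figure is attached. One would need a rule that counts bleeding as infection, and the documents contain none.

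**The case against.** The best defense is that Appendix C is a recovery form, not the outcome classifier. No text makes an answer on it an SSI, and 30-day readmission has no row on it either, so other data sources must be intended. Patients are told to contact the hospital whenever signs develop, including between visits. There is a Comments line. The protocol says most SSIs are apparent by POD 3-5, which suggests the late share is small.

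A reader might infer three stronger things that the documents do not support:
- *The form records only the state of the wound on the day of the call, so a settled infection must be answered No.* Most rows are tenseless labels, the column heading dates the contact rather than the recall window, and the Follow Up text asks about changes and new symptoms. A settled infection may be missed; it need not be.
- *Such a patient would answer No throughout.* A healed wound gives Yes on the row for a closed, intact incision.
- *Bleeding will be counted as infection and cost power.* Nothing says so, and examination or record review of each Yes would settle the matter.

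What remains is that self-report has no form or classification rule attached, care obtained elsewhere need not reach the team, free text without a prompt is not systematic, and a majority apparent early is not all. The odor, redness and fever rows give context to a Yes on leakage but do not establish an SSI.

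**Conclusion.** The point holds as a weakness in how the primary outcome is captured. The last scheduled SSI contact uses a form with no recall period, no item on diagnosis or treatment since the previous visit, and a leakage row that is not specific to infection. Late SSIs that have settled may be missed.

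The size is not known. The fall in power from 79.9% to 77.5-72.1% is an illustration that rests on an assumed 5-15% loss, equal in both arms, and on a two-sided uncorrected test. At the low end it costs 2.4 points, which is minor. The plan has little slack, however: power starts at about 80%, and no dropout allowance is stated. This is a worthwhile, inexpensive correction and not a flaw that undermines the design.

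**What to change.** Revise Appendix C, and the matching Follow Up text, in four respects:

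1. Ask each sign as *at any time since your POD 12-14 visit*, with date of onset and whether it is still present.
2. Split the leakage row into pus and blood, following the distinction already made in Appendix B.
3. Add: *has anyone opened or drained the incision, or prescribed antibiotics for it (date, place)?*
4. State that any Yes is classified from the medical record under the CDC/NHSN definition already named for the primary outcome.

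The cost is new form wording, about one more minute on a planned call, and retrieval of records for patients who answer Yes. Some recall error will remain. Treatment, visits and sample size are unchanged.
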